4.4 Sample size calculation

Based on previous studies in patients treated with SGLT2 inhibitors, we expect a change in systolic blood pressure of 6-8 mmHg during normal sodium intake (150 mmol/day) (6,7). Based on our hypothesis, this effect is increased on a low-sodium intake and reduced during high-sodium intake.

We expect a difference of 4 mmHg between the placebo-controlled effects of ertugliflozin on a low- versus high-sodium diet, with a conservative SD on this difference of 8 mmHg.

A total of 34 patients completing the study provide 80% power at a two-sided alpha of 0.05, to detect a 4 mmHg difference with the indicated SD of 8 mmHg. Drop-outs will be replaced.

Based on the RED study (7) and DAPASALT(6) study, the power needed to detect changes in GFR and hematocrit are of sufficient magnitude and therefore we expect sufficient power for these parameters as well. **We will include 34 individuals.**

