While it was previously thought that sodium sensitivity is exclusively driven by differences in renal sodium excretion, in salt-resistant people, sodium may bind non-osmotically in tissues such as endothelial surface layers and the glycocalyx, preventing water retention and hypertension (23). Integrity of the endothelial surface layer is important for vascular dynamics, and glycocalyx injuries have been implicated in the progression of DKD and cardiovascular disease. Interestingly, the SGLT2 inhibitor empagliflozin was shown to decrease tissue sodium content as measured by MRI, which could theoretically reduce non-osmotic sodium storage (24). On the other hand, SGLT2-inhibitor induced improvements in endothelial function could drive opposite effects with improved non-osmotic sodium storage. Currently, the effects of SGLT2 inhibition on sodium sensitivity are unknown, while its effect on sodium sensitivity may become very relevant in people that consume excess sodium. Given the blood pressure lowering effects of SGLT2-inhibitors, that may be driven by improvements in endothelial function, one could hypothesize that SGLT2 reduce sodium sensitivity.

Dietary sodium intake may modulate the effects of SGLT2 on the kidney and beyond through several mechanisms, as excessive sodium intake has kidney hemodynamic effects. As such, high sodium intake has been shown to increase GFR and effective renal plasma flow (ERPF) in normoglycemic individuals, while blood pressure (MAP) increased to a smaller extent. Given that renal vascular resistance = $MAP/ERPF$, this parameter declined. Filtration fraction ($FF=GFR/ERPF$) increased in the overweight individuals, but not in lean persons (25). As people with T2D are almost all overweight or obese and are usually sensitive to the effects of high-sodium intake (26), the renal hemodynamic effects of SGLT2 inhibitors could be off-set by high sodium intake. This could be secondary to impairment of tubuloglomerular feedback as shown recently for ertugliflozin in rodent studies (27). In addition, given the potential beneficial effect of SGLT2 inhibitors on kidney oxygenation, large amounts of filtered sodium could off-set this mechanisms of action.

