2. OBJECTIVES

2.1 Primary objective:

1: To investigate the modifying effects of WHO-recommended sodium intake (90 mmol per day) vs. high sodium intake (targeted at 250 mmol per day) on the effect of ertugliflozin 15 mg daily, versus placebo, on 24-hour blood pressure in overweight/obese adults with type 2 diabetes.

2.2 Secondary objective:

To investigate the efficacy of ertugliflozin 15 mg daily, versus placebo, in overweight/obese adults with type 2 diabetes to reduce the hypertensive effects of a high-sodium diet (250 mmol per day) versus 24-hour blood pressure measurement during participant's normal diet (170 mmol/per day) obtained at screening visit.

[figure not shown]

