10. STATISTICAL ANALYSIS

Sample size calculations

The primary endpoint of the study is to investigate the modifying effects of WHO-recommended sodium intake (90 mmol per day) vs. high sodium intake (targeted at 250 mmol per day) on the effect of ertugliflozin 15 mg daily, versus placebo, on 24-hour blood pressure in overweight/obese adults with type 2 diabetes.

Based on previous studies in patients treated with SGLT2 inhibitors, we expect a change in systolic blood pressure of 6-8 mmHg during normal sodium intake (150 mmol/day) [PMID: 33318125; PMID: 23668478]. Based on our hypothesis, this effect is increased on a low-sodium intake and reduced during high-sodium intake.

We expect a difference of 4 mmHg between the placebo-controlled effects of ertugliflozin on a low- versus high-sodium diet, with a conservative SD on this difference of 8 mmHg.

A total of 34 patients completing the study provide 80% power at a two-sided alpha of 0.05, to detect a 4 mmHg difference with the indicated SD of 8 mmHg. Drop-outs will be replaced. Based on the RED study and DAPASALT study, the power needed to detect changes in eGFR and hematocrit are of sufficient magnitude and therefore we expect sufficient power for these parameters as well. The calculation is based on a paired design. The sample size was calculated using Stata-Software (v. 11.2, College station, TX, USA).

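### The sizing hypothesis implies a steeper sodium response on ertugliflozin, while the secondary endpoint would score any blood pressure lowering on high sodium as reduced sodium sensitivity

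*Combined protocol and SAP*

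**What the plan says.** Section 4.4, repeated under Sample size calculations in section 10, starts from an expected drug effect of 6-8 mmHg systolic at 150 mmol/day and adds: "Based on our hypothesis, this effect is increased on a low-sodium intake and reduced during high-sodium intake". The size follows: "We expect a difference of 4 mmHg between the placebo-controlled effects of ertugliflozin on a low- versus high-sodium diet". The SD assumed for it is 8 mmHg, which the plan describes as cautious. The result is "A total of 34 patients completing the study provide 80% power at a two-sided alpha of 0.05", and section 10 adds "The calculation is based on a paired design".

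The Introduction approaches sodium from the other side. After noting that the effect of SGLT2 inhibition on sodium sensitivity is not known, it says that "one could hypothesize that SGLT2 reduce sodium sensitivity". The secondary objective (2.2, repeated in 8.1.2) is to show that ertugliflozin can act "to reduce the hypertensive effects of a high-sodium diet (250 mmol per day"), judged against the 24-hour recording made on the usual diet at screening. The sodium-sensitivity item in section 8.3 uses the same reference: blood pressure on the high-sodium diet less that at screening, compared between drug and placebo. Section 10.2 compares the increments on high sodium between the two treatments but does not name the reference value.

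**The concern.** The primary and secondary questions use the same high-sodium recordings, and their expected directions are set out in different places without being related to each other. A drug that works less well on high sodium is a drug on which sodium raises blood pressure more. A reader who holds the sizing hypothesis next to the Introduction therefore finds two opposite expectations about sodium sensitivity in the everyday sense, which is the change in blood pressure per change in intake within a treatment.

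What is at stake is interpretation rather than power. The trial exists to explain a mechanism. If sodium sensitivity is not defined once and with a sign, the same 34 patients can be reported as showing that high sodium weakens the drug and also that the drug reduces sodium sensitivity.

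**Working it through.** **Inputs.** Interaction 4 mmHg, SD of that difference 8 mmHg, n = 34, two-sided alpha 0.05, drug effect 6-8 mmHg at 150 mmol/day (4.4 and 10). Diets of 90 and 250 mmol/day (2.1). Sodium sensitivity measured against one screening recording taken before any diet block or study drug (8.3).

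**1. The plan's own figure.** Paired t-test on the within-patient double difference: noncentrality (4/8) x sqrt(34) = 2.92 on 33 degrees of freedom. Power is 80.8% at n = 34 and 79.5% at n = 33, so 34 is the smallest adequate number. The figure reproduces.

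**2. What the primary contrast measures.** Let PL, PH, EL and EH be mean blood pressure on placebo (P) or ertugliflozin (E), on low (L) or high (H) sodium. Let dL = PL - EL and dH = PH - EH be the drug effects. Then

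dL - dH = (PL - EL) - (PH - EH) = (EH - EL) - (PH - PL).

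The left side is the sizing contrast, +4 mmHg. The right side is the rise from 90 to 250 mmol/day on drug minus the rise on placebo. They are the same number, whatever the placebo rise is.

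**3. What the secondary contrast measures.** With S the single screening value,

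(EH - S) - (PH - S) = EH - PH = -dH.

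S cancels. What remains is the drug effect on the high-sodium diet, with no information on the slope.

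**4. Both contrasts under the sizing scenario.** The documents do not say how the 4 mmHg divides around 6-8 mmHg, so three splits are shown. For the linear one the slope is 4/160 = 0.025 mmHg per mmol. That gives 6 + 0.025 x 60 = 7.5 and 8 + 1.5 = 9.5 on low sodium, and 6 - 0.025 x 100 = 3.5 and 8 - 2.5 = 5.5 on high sodium.

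| Split (assumed) | dL | dH | 90-to-250 response, drug minus placebo | Sodium sensitivity by 8.3, drug minus placebo |
|---|---|---|---|---|
| Equal | 8-10 | 4-6 | +4 | -4 to -6 |
| Linear in sodium | 7.5-9.5 | 3.5-5.5 | +4 | -3.5 to -5.5 |
| All lost on high sodium | 6-8 | 2-4 | +4 | -2 to -4 |

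An illustration with invented levels, which drop out of both contrasts: PL 130, S 132.5, PH 135, linear split around 7 mmHg (dL 8.5, dH 4.5). Then EL = 121.5 and EH = 130.5. The low-to-high rise is 5 on placebo and 9 on drug, so it is 4 larger on drug. Against screening the changes are +2.5 on placebo and -2.0 on drug, so 4.5 lower on drug.

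**5. How often both are significant.** Assume four independent condition residuals of SD 4. The double difference then has SD 4 x sqrt(4) = 8, as planned, and a single drug contrast has SD 4 x sqrt(2) = 5.66. Simulation used 20,000 trials of 34 patients per scenario. The primary is positive in about 81% throughout.

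| dH | Power for EH - PH, SD 5.66 | Both significant | Power for EH - PH if its SD is 8 |
|---|---|---|---|
| 2 | 52% | 35% | 29% |
| 3.5 | 94% | 75% | 70% |
| 4 | 98% | 79% | 81% |
| 5.5 | >99.9% | 81% | 97% |

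A significant secondary result in the wrong direction did not occur in any scenario. With SD 8 on the single contrast, joint significance cannot exceed the power of either test, so at most 70% at 3.5 mmHg and 29% at 2 mmHg.

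**The case against.** A reader might infer from step 2 that the trial is powered to refute its own second hypothesis, or that the two hypotheses cannot both be true. The documents do not support that. Sections 2.2, 8.1.2 and 8.3 set the high-sodium value against usual diet at screening, not against the 90 mmol/day diet. By step 3, any dH above zero supports the secondary hypothesis so defined, and the sizing scenario implies a dH of about 2-6 mmHg. It therefore tends to confirm both. The contradiction appears only when a within-treatment reference replaces the one in the protocol. Extrapolating a drug-related change over 170 to 250 mmol/day does not rescue the stronger reading either, because no on-drug recording at usual intake is planned.

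Three further points are fair. The Introduction's wording is tentative, it describes mechanisms in both directions, and section 8.3 names hypothesis 2 neutrally. Testing is two-sided, so power is the same 80.8% for an interaction of -4 mmHg. Two figures are missing from the text available, and a diagram might address direction.

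These points dispose of the stronger reading but not of the labelling problem. Because the screening value cancels, the secondary contrast cannot tell a blunted sodium response from ordinary blood pressure lowering, yet the protocol calls it sodium sensitivity. Section 10.2 leaves the reference open. If its increments are read as high versus low sodium within each treatment, the secondary becomes the primary interaction with the opposite expected sign.

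**Conclusion.** The point holds in this form. The 4 mmHg sizing hypothesis is exactly a 4 mmHg greater 90-to-250 mmol/day response on ertugliflozin than on placebo, against the Introduction's suggestion, and the readable text does not acknowledge it. This needs no assumption.

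The practical consequence is that section 8.3, followed as written, would score any lowering on high sodium as reduced sodium sensitivity, including when the randomised comparison in the same patients shows it increased. The chance of that pairing, 75-81% for a dH of 3.5-5.5 mmHg and 35% at 2 mmHg, rests on independent, equal residuals of SD 4 and on the assumed split of the 4 mmHg. The documents give neither. The sample size is unaffected. The plan should be changed, because the defect bears on what the trial may claim.

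**What to change.** - In 10.1, state that the primary interaction (EH - EL) - (PH - PL) is also the within-treatment sodium-sensitivity contrast. Give its sign: positive means a smaller drug effect on high sodium and greater sodium sensitivity on ertugliflozin.
- In 8.3 and 10.2, keep EH - PH as the secondary estimate but call it the drug effect on the high-sodium diet. Name the reference in 10.2.
- Allow a claim of reduced sodium sensitivity only if the interaction is in that direction.
- Reconcile the Introduction, 2.2 (with 8.1.2), 4.4 (with section 10), 8.3 and 10.2, so that one definition and one expected direction run through the protocol.

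The cost is wording and the relabelling of an estimate that is already planned. No patients, visits or measurements are added, and n = 34 stands. The downside is that the secondary result alone will no longer support a statement about sodium sensitivity.

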5. TREATMENT OF SUBJECTS

5.1 Investigational product/treatment

In addition to their ongoing oral glucose-lowering medication (metformin or a SU-derivative) and drugs for cardiovascular risk management (e.g. ARB and/or statin), subjects will randomly be assigned to receive ertugliflozin 15mg or a matched placebo treatment during the first intervention phase of the study. Following a wash-out phase the participants will then start with the second intervention phase and receive the other study medication (see table 1).

Table 1. Overview treatment allocation

Product and dosage	Dosage form and strength	Manufacturer
Ertugliflozin 15mg QD	15 mg tablets (orally)	Merck
Placebo ertugliflozin-matching tablet QD	Matched tablets (orally)	Merck

The study medication (ertugliflozin and matching placebo) will be provided by Merck. The pharmacy department of Amsterdam UMC, location VUMC, will be responsible for randomization and distribution of study medication.

Study medication details: ertugliflozin (Steglatro® by Merck Sharp & Dohme BV., USA). Ertugliflozin L-pyroglyutamic acid: (1S,2S,3S,4R,5S)-5-(4-chloro-3-(4-ethoxybenzyl)phenyl)-1-(hydroxymethyl)-6,8-dioxabicyclo[3.2.1]octane-2,3,4-triol, compound with (2S)-5-oxopyrrolidine-2-carboxylic acid.

5.2 Use of co-intervention (if applicable)

During the treatment phases, participants will be subjected to a sodium diet. While a regular sodium intake in the Netherlands, based on previous studies and literature, is around 170 mmol/day; we will coach participants by providing food lists and counselling, to lower their intake to WHO-recommended amounts of 90 mmol/day. This will be done during 10 days prior to start study medication (compliance checked by 24-hour sodium analysis) and during the 10-day intervention. Thus for a total of 20 days per treatment block. Low-sodium intake will be effected during both ertugliflozin and placebo. Similarly, using dietary counselling, participants will be instructed to follow a high-sodium diet aimed at 250 mmol/day.

5.3 Escape medication

Not applicable

6. INVESTIGATIONAL PRODUCT

6.1 Name and description of investigational product(s)

Study medication details: ertugliflozin (Steglatro® by Merck Sharp& Dohme BV., USA). Ertugliflozin L-pyroglyutamic acid: (1S,2S,3S,4R,5S)-5-(4-chloro-3-(4-ethoxybenzyl)phenyl)-1-(hydroxymethyl)-6,8-dioxabicyclo[3.2.1]octane-2,3,4-triol, compound with (2S)-5-oxopyrrolidine-2-carboxylic acid.

6.2 Summary of findings from non-clinical studies

Please refer to the IB

6.3 Summary of findings from clinical studies

Please refer to the IB

6.4 Summary of known and potential risks and benefits

Please refer to the IB.

In addition, a structured risk analysis is provided in chapter 13.

6.5 Description and justification of route of administration and dosage

The standard clinical dosage is 15 mg once daily. It is oral administration. Please refer to IB.

6.6 Dosages, dosage modifications and method of administration

The dosage in this study is 15 mg once daily, oral. This is conform the manufacturer's instructions and what has been extensively studies in clinical trials.

6.7 Preparation and labelling of Investigational Medicinal Product

The investigational product (ertugliflozin and placebo) are provided by MSD according to GMP production. Labelling will be done in collaboration with the trial pharmacy at Amsterdam UMC.

6.8 Drug accountability

Medication is shipped to both study sites by MSD and will be received by the trial pharmacy at Amsterdam UMC according to guidelines.

Randomization

The treatment assignment will be performed by the trial pharmacists of Amsterdam UMC-location VUmc (who have ample experience with this process), in order to maintain blinding for the investigator, site personnel, and patients. A randomization sequence will be generated and sent through an automated system (Castor EDC) by the investigator to the trial pharmacy, ensuring that the investigator remains blinded.

Labeling, Drug dispensation, and Accountability

Merck will provide the trial drug and the placebo. The trial products will be labelled with participant identifying information to our institutional trial pharmacist, who subsequently will store the trial products according to prevailing guidance until they are needed. The trial pharmacist will deliver the study medication to the research personnel (who remain blinded). These will then dispense the study medication to the participants at the designated visits, combined with extensive instructions on use and administration of the study drug. The number of daily dosages dispensed will be sufficient to cover the complete expenditure of the study. No trial products will be dispensed to any person not enrolled in the trial.

On the designated days, the participants will bring their trial medication. In order to perform proper drug accountability, the investigator will keep track of all received, used and unused trial products and -if possible- all empty packaging. Non-used medication will be returned to the pharmacy department where it will be destroyed.

Drug storage

Ertugliflozin does not require any special storage conditions (Agency, 2018).

Nevertheless, when not distributed to participants, drugs will be stored at the institutional trial pharmacy. Proper storage conditions will be ensured and records and evaluations will be kept as required by International Conference on Harmonisation – Good Clinical Practice (ICH-GCP).

Blinding and Unblinding

Throughout the study duration, all study personnel will remain blinded with regard to the medication used. The randomization –in order to achieve blinding for study personnel- will be performed by the trial pharmacist of the Amsterdam UMC-VUmc. The investigator will receive the subjects blinding information concerning the study medication in the form of a sealed envelope; this envelope will be stored on a secure location in the Diabetes Center Amsterdam UMC-VUmc. The blind shall not be broken by the investigator unless information concerning the study medication is necessary for the medical treatment of the subjects. Procedures regarding emergency unblinding are described in Chapter 9. If the investigator is unblinded, study medication will be stopped immediately in addition to the withdrawal of the study subject from the study. At the end of the study, following the last patients last visit and database lock (which will only occur after medical / scientific review), the blind will be broken by the trial pharmacist.

7. NON-INVESTIGATIONAL PRODUCT

7.1 Name and description of non-investigational product(s)

Iohexol (Omnipaque® by GE Healthcare B.V.) (1)

Supplied as: 200 mL ampoules with a clear, colorless solution containing 300 mg iohexol per mL.

Approved agent: Approved by the Dutch drug authority (College ter Beoordeling van Geneesmiddelen; RVG 09821)

Action: Iohexol is a non-ionic, monomeric, triiodinated, water-soluble substance mostly used as X-ray contrast medium. In the concentration of 140 mg I/ml it is isotonic with blood and tissue fluid. Close to 100 per cent of the intravenously injected iohexol is excreted unchanged through the kidneys within 24 hours in patients with normal renal function. The maximum urinary concentration of iohexol appears within approximately 1 hour after injection. No metabolites have been detected. The protein binding of iohexol is very low (less than 2%).

Side effects: The risk of serious reactions in connection with use of Omnipaque is regarded as minor. However, iodinated contrast media may provoke serious, life-threatening, fatal anaphylactic/anaphylactoid reactions or other manifestations of hypersensitivity.

Dosing: For the steady-state iohexol-clearance test, an initial bolus dose is given, followed by continuous infusion with a dose calculated to maintain the plasma concentration between 100 mg/L and 150 mg/L.

Storage: Iohexol can be stored up to 3 years below 30°C.

Sodium-4 amino hippurate (PAH, Basic Pharma Manufacturing BV) (2)

Supplied as: PAH is supplied as single use vials of 10mL vials containing sterile 20% (2g/10mL) of 4-Aminohippuric acid dissolved with one equivalent of sodium hydroxide using water for injection.

Approved agent: An authorized PAH, USP Grade, manufactured by Merck, was available for research for the estimation of ERPF. However, the authorized product was removed from the market in the late '90s/ early 20's and is no longer available for use in clinical trials. PAH manufactured by Basic Pharma does not yet have marketing authorization in an ICH country.

Action: PAH is a derivative of hippuric acid, which is derived from the amino acid glycine. It is inert in normal doses.

Side effects: Extremely large doses may cause osmotic diuresis. Some patients may have a sensation of warmth, or the desire to urinate or defaecate during or shortly following the infusion. Allergic and anaphylactic reactions have been reported with the PAH produced via Merck but were very uncommon.

Dosing: During one PAH-clearance test, an initial bolus will be given followed by a continuous infusion with a dose calculated to maintain the plasma concentration between 15mg/L and 20mg/L.

Storage: PAH will be stored at room temperature protected from light.

7.2 Summary of findings from non-clinical studies

Please refer to IB

7.3 Summary of findings from clinical studies

Please refer to IB

7.4 Summary of known and potential risks and benefits

See above and in the structured risk analysis. At our research centre at Amsterdam UMC we have done > 500 iohexol and PAH clearances in the last 5 years and not encountered a single problem.

7.5 Description and justification of route of administration and dosage

Intravenous usage. Dosage are indicated above.

7.6 Dosages, dosage modifications and method of administration

Please see above.

